has been reported that although nasal high-flow oxygen therapy can reduce the incidence of hypoxia in ordinary patients during painless gastroscopy, its effect on improving ventilation in OSAHS patients is relatively limited [3-4]. Painless gastroenteroscopy has been widely used in the diagnosis and treatment of digestive tract diseases, during which the occurrence of intraoperative hypoxia is also concerned. At present, nasal catheter oxygen delivery is widely used clinically to prevent the occurrence of intraoperative hypoxia [5]. In addition, studies have shown that carbon dioxide monitoring can reduce the incidence of hypoxemia, but cannot avoid the occurrence of severe hypoxia [6]. However, hypoxia still occurred during the operation (8%) after the application of low flow nasal catheter [7]. Previous studies have shown that although new devices such as high-flow nasal catheter oxygen inhalation and supraglottal airway injection technology can reduce the incidence of hypoxia, they are difficult to be widely used in clinical practice due to high cost and inconvenience [8,9]. Supraglottic jet ventilation devices can reduce the incidence of hypoxia from 9% to 3% [10], but they are costly, prone to adverse events such as nosebleeds, and troublesome to use. High oxygen flow can increase FiO₂ to 1.00 and maintain slight PEEP, and produce the effect of dead cavity flushing [11], which further reduces the incidence of hypoxia and increases the minimum oxygen saturation [12], but it is expensive and prone to adverse reactions such as airway dryness, pharyngeal pain and barotrauma [9]. The oropharyngeal airway is an important airway auxiliary device for short-term airway management during the perianesthetic period, which can provide patients with an unobtrusive airway during autonomous ventilation [12]. The oropharyngeal vent has been proven to be successfully used in infants, the elderly and MRI examinations, and can be used in short outpatient surgery instead of laryngeal mask [13]. The oropharyngeal airway has a low incidence of pharyngeal trauma and laryngeal pain immediately after surgery, requiring a shorter exposure time of inhaled anesthetic and a lower concentration of propofol to successfully place it [14]. During the operation to preserve spontaneous breathing, the oropharyngeal airway is introduced as a ventilation device [15]. The new oropharyngeal airway can accept the implantation of gastroscopy and provide oxygen to patients without affecting the operation at the same time. In order to explore whether the new oropharyngeal airway can provide better oxygen to patients undergoing painless gastroenteroscopy and reduce the incidence of hypoxia during the operation, we have drafted this study and explored the safety of the new oropharyngeal airway in painless gastroenteroscopy.

By combining precision medicine with comfortable diagnosis and treatment, painless gastroscopy has become the first choice for the diagnosis and treatment of upper gastrointestinal diseases. Propofol is widely used in painless gastroscopy because of its rapid onset and rapid elimination, but the incidence of hypoxemia is high, which is related to the easy cause of apnea and abnormal ventilation of patients with propofol. Obstructive sleep apnea hypopnea syndrome is a potentially dangerous disease, and is one of the common causes of sudden cardiac death and stroke in clinical practice [1]. OSAHS patients, especially those with severe (AHI > 40), have repeated apnea at night, resulting in a long-term state of low blood oxygen at night and serious lack of sleep, and their tolerance to surgery and anesthesia drugs has decreased significantly, especially when accompanied by hypertension, asymptomatic cerebral embolism and other complications, the risk of surgery is greater. Death after operation has been reported at home and abroad [2]. However, most severe OSAHS patients not only have palatopharyngeal plane obstruction, but also have multiple plane obstruction at the same time. In order to improve the surgical success rate of OSAHS patients with multiplane obstruction of upper airway, it is necessary to implement comprehensive treatment based on simultaneous combined multiplane surgery for severe OSAHS patients with multiplane obstruction to improve the curative effect, which has been a consensus at present. However, this may cause higher level of postoperative upper airway asphyxia, which puts forward higher requirements for postoperative upper airway management. In order to improve the surgical success rate of OSAHS patients with multi-plane obstruction of upper airway, reduce postoperative respiratory complications, and alleviate patients' pain, nasopharyngeal airway airway and oropharyngeal airway airway are generally recognized as the best methods for postoperative respiratory management. Due to a large amount of fat accumulation in the chest and abdomen of the patient, the total compliance of the chest and lungs is reduced. The lower position of the intubation head under general anesthesia and abdominal surgery will lead to further upward movement of the diaphragm, resulting in decreased thoracic volume, reduced total compliance of the chest and lung, decreased functional residual chest volume, premature closure of small airways, and reduced number of ventilation alveoli. At the same time, the abdominal venous blood is squeezed into the thoracic vein during abdominal surgery, resulting in the accumulation of blood in the chest and the increase of physiologically ineffective cavities, resulting in a decrease in the ventilation/blood flow ratio [3]. Airway management in OSA patients is difficult due to excessive fat accumulation in the front neck, lower neck and chest, which leads to limited movement of the neck. In addition, there may be excess tissue in the throat, which leads to airway stenosis. Especially for patients with OSA, induced intubation

must be avoided and conscious intubation under surface anesthesia or guided intubation under fiberoptic bronchoscope should be adopted [4]. To sum up, airway management in obese patients is a clinical focus and difficulty. In order to reduce the trauma of patients and promote ERAS, endotracheal intubation is often not possible during the operation of painless gastroenteroscopy. Therefore, it is a topic worthy of our exploration to not only meet the comfort requirements of patients, but also ensure the safety of patients during the whole perioperative period. Whether the birth of new oropharyngeal airway can solve the ventilation problem of obese patients during anesthesia is the significance of this research.

【reference】

- [1] Zeng Shiying, ZHANG Longyu, ZHAO Xinyuan, ZHANG Jin, BAI Junyun. Effect of nasal continuous positive airway pressure on patients with obstructive sleep apnea syndrome [J]. World Journal of Sleep Medicine, 2021, 8(03):537-538.
- [2] Pang Congyi, Yi Jingde. Effect of nasal continuous positive airway pressure on patients with chronic heart failure complicated with obstructive sleep apnea hypopnea syndrome [J]. Medical food therapy and health, 2021, 19(12):48-49.
- [3] Liu Xiaojie, Li Dajiang, Ning Jishun, et al. A case of severe hypoxemia in obese patients undergoing radical general anesthesia for colon cancer [J]. Journal of Clinical Anesthesiology, 2016, 32(05):518.
- [4] Hang Yannan. Handbook of Contemporary Anesthesia [M]. 2nd Ed. Beijing: World Book Publishing House, 2011: 358-363.

Research content:

1. Study population

The principal investigator was responsible for recruitment under strict control, and 130 patients with obstructive sleep apnea hypopnea syndrome (diagnosed as OSAHS by polysomnography monitoring) who underwent painless gastrocolonoscopy from today were selected. They were informed and consented to this clinical trial.

2. Sample size calculation:

According to the pre-test results, the incidence of hypoxia in the test group and the control group were 0.2 and 0.5, respectively. The sample size was calculated using PASS software, and the bilateral test level $\alpha=0.05$ and the test efficacy power=0.9

were set. 52 cases were required in each group according to the incidence of hypoxia, and 65 cases in each group were calculated after considering 20% shedding rate, totaling 130 cases.

3. Specific research content:

Study participants entered the examination room to establish intravenous access, using 2% lidocaine gel 5ml containing mouth cavity and pharynx. Heart rate (HR), pulse oxygen saturation (SpO₂), end-expiratory carbon dioxide, IPI (composite lung index), ECG monitoring, and non-invasive blood pressure (measured every 2.5 minutes) were routinely monitored before anesthesia induction. Ask patient to lie on left side.

In this study, the investigators planned to implement simple randomization using SAS:

(1) The group using the new oropharyngeal airway (test group) : Oxygen was continuously supplied through a catheter partially attached to the endoscopic mouth before induction of anesthesia until the end of gastroenteroscopy.

(2) In the conventional endoscopic bite group (control group), oxygen was continuously supplied through a common nasal catheter before induction of anesthesia until the end of gastroenteroscopy.

The entire trial operation process was completed by the investigators participating in the clinical trial. Before induction of anesthesia, study participants in the experimental group received 5-6L/min of oxygen for about 1 minute through an endoscopic biting oxygen supply device, and participants in the control group inhaled 5-6L/min of oxygen for about 1 minute through a nasal catheter. Propofol 3mg/kg and sufentanil 7 μ g were used to induce anesthesia in both groups. Sufentanil was given at the beginning of pre-oxygen inhalation, and propofol was given 1min later. When participants achieved sufficient sedation (about BIS40), the new oropharyngeal airway group was placed into the oropharyngeal airway through the endoscopic bite and then began gastroscopy. The ordinary endoscopic bite group began to perform endoscopic operation after sufficient sedation was achieved. In both groups, 5mg/kg·h propofol was injected continuously to maintain anesthesia until the examination was completed. If participants showed frowning or slight body movement during diagnosis and treatment, 40 to 50mg of propofol was added intravenously. If HR < 50 times/intravenous injection of atropine 0.5mg; MAP < 60mmHg intravenous hydroxyamine 1mg; When SpO₂ < 92%, artificial airway intervention such as jaw support, assisted breathing or mask was given. After the examination, study participants were not allowed to leave the examination room until they had a

MOAA/S score of 3-4. If the sedation/anaesthesia Discharge rating scale scores more than 9 points, patients can be accompanied by relatives and friends. The incidence of hypoxia ($75\% \leq \text{SpO}_2 < 90\%$, $\leq 60\text{s}$) and severe hypoxia ($\text{SpO}_2 < 75\%$ or $75\% \leq \text{SpO}_2 < 90\%$, $\geq 60\text{s}$) during anesthesia were recorded. The incidence of choking, reflux aspiration and laryngeal spasm were recorded. The time of intervention was half or disappearance of end-expiratory carbon dioxide and/or disappearance of thoracic fluctuation and/or $\text{SpO}_2 < 95\%$, that is, opening the airway successively until $\text{SpO}_2 \geq 95\%$, and recording the last means of opening the airway.

The means of opening the airway of the two groups were the same, including: 1) adjusting the oxygen flow; 2) Lift the lower jaw; 3) Mask ventilation (pull out the gastroscope if necessary); 4) Tracheal intubation or laryngeal mask for ventilator assisted ventilation.

Patient satisfaction scales usually use a 0-10 scale, where 0 is very dissatisfied and 10 is very satisfied. Patients are asked to select a number on the rating scale to indicate satisfaction with medical services or pain relief methods based on their actual experience;

The doctor satisfaction scale also uses a 0-10 scale, with 0 being very dissatisfied and 10 being very satisfied. Endoscopists need to select a corresponding number on the score sheet according to their actual experience to indicate whether the patient is satisfied with the cooperation and response of the operation process.

五、Research Methods

1. Inclusion criteria

130 patients with obstructive sleep apnea hypopnea syndrome who underwent painless gastroenteroscopy in our hospital from now on were selected.

1.1 Inclusion criteria:

- 1) Age 18-65 years old
- 2) evidence of OSAHS diagnosed by polysleep monitoring
- 3) written informed consent of patient or family member
- 4) painless stomach + colonoscopy
- 5) ASA grade I-II diagnostic criteria for OSAHS: 1) OSAHS diagnosed by polysleep monitoring (PSG). 2. For patients who come to make an appointment for

gastroenteroscopy, the risk assessment results can be given through questionnaires combined with the major risk factors, physical examination, clinical symptoms, etc., which have been identified. For example, the STOP-BANG questionnaire evaluated the risk through eight items including snoring, fatigue, observed apnea, blood pressure, body mass index, age, neck circumference, and gender. For those at higher risk, a diagnosis can be made by providing free polysomnography monitoring (PM) with informed consent.

1.2 Exclusion criteria:

- 1) Patients with blood clotting disorders or a tendency to oropharyngeal bleeding, mucosal damage or space occupation, difficulty in placing oropharyngeal airway, etc., who cannot perform oropharyngeal airway ventilation;
- 2) Upper respiratory tract infections such as mouth, nose or throat;
- 3) Fever (core body temperature $\geq 37.5^{\circ}\text{C}$);
- 4) a confirmed diagnosis of pregnancy or breastfeeding;
- 5) Allergic to sedatives such as propofol or equipment such as tape;
- 6) Emergency surgery;
- 7) Multiple trauma;
- 8) $\text{SpO}_2 < 95\%$ before operation;
- 9) A history of drug and/or alcohol abuse within 2 years prior to the start of the screening period;(Drinking more than three times standard alcoholic beverages per day, equivalent to about 10g of alcohol or equivalent to 50g of Chinese liquor);
- 10) Patients with previous psychiatric and neurological diseases, such as depression, severe central nervous depression, Parkinson's disease, basal ganglia disease, schizophrenia, epilepsy, Alzheimer's disease, myasthenia gravis;
- 11) Currently participating in other clinical trials;
- 12) Patients who are deemed unfit by the investigator to participate in the trial;
- 13) Patients with a history of smoking should not participate in this study.

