Research program	
Heart rate, pulse oxygen saturation (SpO₂), end-expiratory carbon dioxide, ECG monitoring, and noninvasive blood pressure (measured every 3 minutes) were routinely monitored before anesthesia induction. In this study, SAS was used to achieve simple randomization: 1. In the group using the new oropharyngeal airway (test group), oxygen was continuously supplied through a catheter connected to the endoscopic bites until the end of the gastroenteroscopy before induction of anesthesia. 2. In the conventional endoscopic bite group (control group), oxygen was continuously supplied through a conventional nasal catheter before induction of anesthesia and until the end of gastroenteroscopy. Before anesthesia induction, patients in the experimental group received 5-6L/min of oxygen for about 1min through the endoscopic bite connecting oxygen supply device, and patients in the control group inhaled 5-6L/min of oxygen for about 1min through the nasal catheter. Propofol 3mg/kg and sufentanil 7μg were used to induce anesthesia in both groups. Sufentanil was given at the beginning of pre-oxygen inhalation, and propofol was given 1min later. When participants achieved sufficient sedation (about BIS40), the new oropharyngeal airway group was placed into the oropharyngeal airway through the endoscopic bite and then began gastroscopy. The ordinary endoscopic bite group began to perform endoscopic operation after sufficient sedation was achieved. In both groups, 5mg/kg·h propofol was injected continuously to maintain anesthesia until the examination was completed. If participants showed frowning or slight body movement during diagnosis and treatment, 40 to 50mg of propofol was added intravenously. If HR < 50 times/intravenous injection of atropine 0.5mg; MAP < 60mmHg intravenous hydroxyamine 1mg; When SpO₂ < 92%, artificial airway intervention such as jaw support, assisted breathing or mask was given. After the examination is completed, the patient should not leave the examination room until the MOAA/S is 3-4 points. If the sedation/anaesthesia

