1.3 Exclusion/removal criteria

- 1) The patient voluntarily withdrew the informed consent
- 2) the operation was cancelled

2. Grouping of study participants:

This study planned to implement simple randomization with SAS: Group 1 was the group using the new oropharyngeal airway (experimental group);The other group was the control group (control group).

3. Blinded/unblinded patients This study was an open trial, and no blinded method was used.

4. Remedial and supportive treatment (necessary treatment measures for the occurrence of SAE related to the study)

(1) Continue to inject propofol with a range of 5ml to achieve the appropriate depth of anesthesia again if coughing, limb struggle and other conditions occur during the procedure;

(2) If severe airway spasm, obstruction of ventilation occur during the operation, and the airway cannot be effectively improved, measures such as mask pressure oxygen, emergency tracheal intubation or cricothyroid puncture should be taken. In the event of intraoperative emergencies and accidents, patients should be treated primarily, and patients should be put in the first place in accordance with clinical routine rescue and treatment of study participants.

5. Study Participant Early withdrawal/Trial termination criteria: Unconditional termination of the trial at any time when a study participant proposes to withdraw from the trial, while still guaranteeing patient safety throughout the process.

Research program

1. Study Participant Management

1) Study participant recruitment methods: The staff participating in this clinical trial was responsible for recruitment under the control of the principal investigator. 130 patients with obstructive sleep apnea hypopnea syndrome (diagnosed as OSAHS by polysomnography monitoring) who met the enrollment criteria and intended to undergo painless gastrocolonoscopy in our hospital were initially screened, and the recruitment materials were distributed to the study participants and their families.

2) Informed consent process: When enlisting study participants, inform study participants and their families of the detailed contents of the study, possible risks and benefits (see informed consent for details) in accordance with the content and requirements of informed consent, obtain consent from study participants and their families, and sign informed consent before anesthesia induction.

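### Does simple randomization, without blocks or severity strata, weaken this 130-patient trial?

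*Protocol*

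**What the plan says.** The allocation method appears three times in the Protocol, always the same. The Scheme summary (Research program) has "In this study, SAS was used to achieve simple randomization"; Research content, 3. Specific research content, has "the investigators planned to implement simple randomization using SAS"; Research Methods, 2. Grouping of study participants, has "This study planned to implement simple randomization with SAS". No blocks or strata are mentioned. Under Research content, 2. Sample size calculation, "65 cases in each group were calculated after considering 20% shedding rate, totaling 130 cases". Research Methods, 3, adds: "This study was an open trial, and no blinded method was used".

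On severity, Test basis, 2. Study participant selection basis, has the background remark that "OSAHS patients, especially those with severe (AHI > 40), have repeated apnea at night", and links this to poorer tolerance of surgery and anesthetic drugs. Research Methods, 1.1, requires "evidence of OSAHS diagnosed by polysleep monitoring" and adds that "For those at higher risk, a diagnosis can be made by providing free polysomnography monitoring (PM) with informed consent". Nothing there says that the AHI value is recorded, or that it predicts hypoxia during endoscopy.

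The section Statistical analysis plan, 2, gives an unstratified Chi-square or Fisher test for the primary outcome. It says that the full analysis plan will be fixed before database lock.

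**The concern.** A target of 65 per group seems to promise something that coin-toss allocation cannot deliver. At 130 patients the arms can differ visibly in size and in the share of severe cases. The protocol itself singles out severe disease, and every participant must have a sleep study before entry, so a stratifier would often be at hand. An analysis plan can later add an adjustment, but it cannot alter an allocation list already used. If imbalance biased the comparison or cost real power, the primary result would suffer and the list would have to be changed before recruitment.

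**Working it through.** **1. The plan's own figure.** Inputs from the Protocol: rates 0.5 and 0.2, two-sided α 0.05, power 0.9, 20% loss. With the pooled-variance formula and mean rate 0.35,

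n = [1.960·√(2·0.35·0.65) + 1.282·√(0.5·0.5 + 0.2·0.8)]² / 0.3² = (1.322 + 0.821)² / 0.09 ≈ 51.0, rounded up to 52.

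Then 52 / (1 − 0.20) = 65 per group, 130 in total. The figure reproduces. Exact Pearson Chi-square power is 91.0% at 52:52 and 95.9% at 65:65.

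**2. Arm sizes.** One arm's size is Binomial(130, 0.5).
- P(exactly 65) = 0.0698.
- P(smaller arm ≤ 57) = 0.1881.
- The 95% range for one arm is 54 to 76.

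**3. What unequal arms cost.** The variance of a difference scales roughly with 1/n₁ + 1/n₂. For 57:73 this is 130/(57·73) = 0.03124, against 2/65 = 0.03077, a rise of 1.5%. Exact power is then:
- 130 evaluable, 57:73: 95.4–95.5%, against 95.9% balanced.
- 104 evaluable, 46:58: 90.3–90.5%, against 91.0% balanced.

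So a split that sounds lopsided costs about half a point and stays above 90%.

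**4. Validity.** Chance imbalance in severity is part of the random variation that the test already allows for. With a true rate of 0.35 in both arms, 40% severe and a severity odds ratio (OR) of 1, 2 or 5, the simulated type I error of simple randomization with the Chi-square is 5.1% each time. There is no bias to repair.

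**5. What severity could add.** Simulated power: 130 randomized, 20% independent loss, overall rates held at 0.5 and 0.2, 400,000 runs per cell. The severe share and the OR are assumptions. A = simple list with Chi-square (the plan); B = simple list with a Mantel-Haenszel test; C = severity-stratified blocks of 4 or 6 with the same Mantel-Haenszel test.

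| Severe share | OR | A % | B % | C % | Analysis (B−A) | Allocation (C−B) | Total |
|---|---|---|---|---|---|---|---|
| 10% | 1 | 90.46 | 90.04 | 90.44 | −0.4 | +0.4 | 0.0 |
| 10% | 2 | 90.59 | 90.37 | 90.68 | −0.2 | +0.3 | +0.1 |
| 10% | 3 | 90.52 | 90.79 | 91.21 | +0.3 | +0.4 | +0.7 |
| 10% | 5 | 90.47 | 91.48 | 91.96 | +1.0 | +0.5 | +1.5 |
| 40% | 1 | 90.52 | 90.05 | 90.48 | −0.5 | +0.4 | 0.0 |
| 40% | 2 | 90.55 | 90.76 | 91.24 | +0.2 | +0.5 | +0.7 |
| 40% | 3 | 90.60 | 91.79 | 92.13 | +1.2 | +0.3 | +1.5 |
| 40% | 5 | 90.52 | 93.39 | 93.73 | +2.9 | +0.3 | +3.2 |

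With 20% severe the totals at OR 1, 2, 3 and 5 are −0.1, +0.4, +1.1 and +2.3. Column A never leaves 90.5–90.6%. The allocation change is worth 0.3–0.5 points beyond a stratified analysis, and where the total is large the analysis supplies nearly all of it (2.9 of 3.2). Stratified blocks with the planned Chi-square gain 0.1–1.3 points over A, but that test then turns conservative (type I error 3.9% at OR 5 with 40% severe).

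**6. What blocks would cost.** The trial is open and runs in one hospital. Under simple randomization from a concealed list, past assignments say nothing about the next, so a guess is right 50% of the time. Under two severity strata with blocks of 4 or 6 in random order, guessing the arm that is behind in the stratum is right in 69% of cases (simulated; the same at 10%, 20% and 40% severe). The guesser need not know the block size. Research Methods, 1.2, leaves room to act on a guess: it excludes patients whom the investigator judges unsuitable or in whom the airway is hard to place.

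**The case for a change.** The best case for changing the list is that it is inexpensive and cannot be done later. Stratified blocks with a matching test lose at most about 0.1 power points even if severity is irrelevant. They cut the 95th percentile of the gap in arm sizes from 22 patients to 2. If 10%, 20% or 40% are severe, simple randomization leaves the severe share 10 points or more apart in 6%, 16% or 25% of trials; at randomization, stratified blocks bring this to 0%. In a small open trial, a visible imbalance in disease severity invites doubt from readers.

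Those figures stand, and a statistician who prefers stratified blocks here would be making a defensible choice. They do not show that the present choice is wrong. An uneven baseline table is a matter of presentation when the test is valid, and a prespecified adjustment can answer it. After 20% loss, the stratified design still leaves a gap of 10 points or more in 0.2%, 1% or 3% of trials among evaluable patients, against 9%, 20% or 30%. The proposal also needs a recorded AHI and a cut-off taken from a background remark. And calling it inexpensive leaves out the predictability in step 6, which varying the block size reduces but does not remove.

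**Conclusion.** The concern does not hold. Simple randomization is stated consistently, is unbiased, keeps the test at about 5%, and gives about 90.5% power after the planned loss, against 90% planned. The 65 per group is a target for the calculation, and missing it by chance costs about half a point at 57:73. Stratified allocation would be worth about 0.3–0.5 points beyond an adjusted analysis, which can still be prespecified. The total of about 3 points needs an assumed OR of 5 with 40% severe, and the protocol supports neither number. Against this stands a guess rate of 69% instead of 50% in an open trial, assuming that staff see earlier assignments and strata. Reasonable statisticians would differ on that trade. The power figures assume the planned rates of 0.5 and 0.2 and loss unrelated to arm or severity.

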	Discharge rating scale scores more than 9 points, patients can be accompanied by relatives and friends. The incidence of hypoxia ($75\% \leq \text{SpO}_2 < 90\%$, $\leq 60\text{s}$) and severe hypoxia ($\text{SpO}_2 < 75\%$ or $75\% \leq \text{SpO}_2 < 90\%$, $\geq 60\text{s}$) during anesthesia were recorded. The incidence of choking, reflux aspiration and laryngeal spasm were recorded. The time of intervention was half or disappearance of end-expiratory carbon dioxide and/or disappearance of thoracic fluctuation and/or $\text{SpO}_2 < 95\%$, that is, open airway manipulation was taken successively until $\text{SpO}_2 \geq 95\%$, and the last means of opening the airway was recorded. The means of opening the airway of the two groups were the same, including: 1) adjusting the oxygen flow; 2) Lift the lower jaw; 3) Mask ventilation (pull out the gastroscope if necessary); 4) Tracheal intubation or laryngeal mask for ventilator assisted ventilation.
Shedding/culling criteria	After postoperative recovery, patients were assessed for adverse reactions. The score of discharge scale after sedation/anesthesia was more than 9 points. Patients could be accompanied by relatives and friends to leave the hospital.
Shedding/culling criteria	Patients who were lost to follow-up, had adverse events, or voluntarily withdrew from the trial
Early exit criteria	Patients with severe airway spasm, obstruction of ventilation, inability to effectively improve airway, and need emergency tracheal intubation or cricothyroid puncture.
Primary outcome measure	Incidence of hypoxia ($75\% \leq \text{SpO}_2 < 90\%$, $\leq 60\text{s}$) during anesthesia and sedation.
Secondary outcome measure	1, severe hypoxia ($\text{SpO}_2 < 75\%$ or $75\% \leq \text{SpO}_2 < 90\%$, $\geq 60\text{s}$) 2, the incidence of airway intervention 3, intraoperative dose of additional drugs 4, endoscopist satisfaction 5, recorded adverse events: choking, laryngeal spasm and reflux aspiration incidence; Apnea or slow breathing episodes (defined as respiratory rate ≤ 6 beats/min); Bradycardia is defined as a heart rate ≤ 50 beats/min. Serious adverse events such as tracheal intubation, non-invasive ventilation, use of vasopressors, and hospitalization are required.

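### The protocol gives airway support at SpO2 <92% and times airway intervention at SpO2 <95% without relating the two, and ties the secondary outcome on airway intervention to neither

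*Protocol*

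**What the plan says.** Two statements govern airway rescue. Both stand in the Scheme summary (Research program) and again in the body (Research content, 3. Specific research content).

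- **The <92% statement.** The body reads: "SpO₂ < 92%, artificial airway intervention such as jaw support, assisted breathing or mask was given". The summary has the same rule.
- **The <95% statement.** The body reads: "The time of intervention was half or disappearance of end-expiratory carbon dioxide and/or disappearance of thoracic fluctuation", and continues "and/or $\text{SpO}_2 < 95\%$, that is, opening the airway successively until $\text{SpO}_2 \geq 95"%. The summary has the same rule: "that is, open airway manipulation was taken successively until" SpO2 is at least 95%.

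The ladder under the second statement begins "1) adjusting the oxygen flow; 2) Lift the lower jaw; 3) Mask ventilation" and ends with intubation or a laryngeal mask. On comparability the body says "The means of opening the airway of the two groups were the same". On data capture it asks for "recording the last means of opening the airway".

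The incidence of airway intervention is listed as a secondary outcome in three places: Scheme summary, Secondary outcome measure; Scheme summary, Safety index; and Objective, 2. Secondary outcome measure. None of them defines the event. Research Methods, item 3, says that the trial is open, and Specific research content has the participating investigators carry out the whole procedure.

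**The concern.** Jaw lift and mask appear under both statements, with different SpO2 values attached. Nothing says whether 92% is a step inside the <95% ladder or a separate rule, and no SpO2 value or time is given for moving from one step of the ladder to the next. Two investigators could each follow a stated rule and treat the same patient differently.

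This matters because use of airway intervention is itself an outcome. If the point at which manual support begins is left to whichever sentence the operator has in mind, the outcome partly measures operator habit. In an open trial that habit could differ between the arms.

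**Working it through.** The point itself involves no stated figure to reproduce. The check is to set the two statements against each other by patient state.

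| State | <95% statement | <92% statement |
|---|---|---|
| SpO2 at least 95%, no CO2 or chest-movement sign | no action | no action |
| CO2 or chest-movement sign, any SpO2 | ladder starts | applies only if SpO2 is also <92% |
| SpO2 92% to <95%, no sign | ladder starts, continues to at least 95% | silent |
| SpO2 <92% | ladder starts or continues | jaw support, assisted breathing or mask given |

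**Where the question arises.** It is confined to the third row, a band of 95 − 92 = 3 SpO2 points. The CO2 and chest-movement triggers are stated expressly and are not in question.

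**A patient in that row.** SpO2 falls to 93%, there is no CO2 or chest-movement sign, oxygen flow is adjusted, and SpO2 stays at 93%.
1. Under the <95% statement the target is not reached, so working through the means in turn leads to jaw lift and then mask.
2. Under the <92% statement, those manoeuvres are called for only at a lower SpO2.
3. One investigator lifts the jaw. Another treats 92% as the point for manual support and waits. Each can point to the protocol.

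**What this does to the outcome.** Two event definitions are compatible with the text.

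| Definition | Jaw lifted at 93% | Oxygen flow only at 93% |
|---|---|---|
| Any of the four means | event | event |
| Means 2 to 4 only | event | no event |

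Under the first definition the two patients count alike. Under the second, the result depends on what the operator chose to do. The protocol does not say which definition applies. Oxygen-flow adjustment is on the list of means for opening the airway, while the examples in the <92% statement are manual or mask support.

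**What recording the last means settles.** It captures the type of intervention reached. It does not capture the trigger, or the SpO2 at which the first manoeuvre was made.

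**Sample size.** It rests on hypoxia rates of 0.2 and 0.5, not on airway intervention. The protocol's 52 per group reproduces (two-sided 0.05, power 0.9, pooled variance), and 52 / (1 − 0.20) = 65 per group, 130 in total. The present point does not touch it.

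**The case against.** The strongest reply is that the statements do not contradict each other. The <92% sentence does not say that support is withheld above 92%, and the <95% sentence expressly fixes a time of intervention. An operator can obey both by starting the ladder below 95% and giving manual support below 92%. This stands: a reader might infer that the start of airway intervention is nowhere fixed, but the ladder does have a stated start. What is left open is when manual or mask support is due within the 3-point band. The staged reading is reasonable, but it is not written down, and continuing the ladder until 95% is regained allows jaw lift or mask above 92%.

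A second reply is that the outcome has an evident data source, since the ladder is described as intervention and the last means is recorded. A reader might infer that no later document could repair the definition. That goes too far: a statistical analysis plan, which is not at hand, could say which recorded means count as an event. It could not standardise when staff acted.

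A third reply is that bias is conjecture, because both statements apply to both arms and the means are said to be the same. This stands as to size and likelihood. Equal means, however, do not settle which start point is used for manual support.

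**Conclusion.** The point holds in limited form and should be fixed. The relation between the two SpO2 values is not stated, so the start of jaw lift or mask is unclear at 92% to <95% without a CO2 or chest-movement sign, and the secondary outcome event is not expressly defined.

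The size of any effect cannot be derived. The documents do not give the number of patients whose lowest SpO2 falls in the band. A reader might use the planned hypoxia rates of 0.2 and 0.5 to count those affected, but patients who reach <90% have passed below both values and do not measure this group.

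A reader might also infer harm to the primary outcome, because both values lie above its 90% limit. The documents do not show such an effect, nor its direction. Triggers above 90% are not in themselves a defect.

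The conclusion assumes that no study document outside the protocol, such as the case report form or a site procedure, already relates the two values. That different practice by arm is possible rests on the open design; nothing in the protocol shows that it would happen.

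**What to change.** - Reconcile the two statements, in both the Scheme summary and Specific research content, into one rule for starting and escalating airway intervention, applied identically in both arms. If stages are meant, say so. The clinical team decides the content.
- Define the secondary outcome event to match that rule, including whether oxygen-flow adjustment alone counts.
- If the case report form does not already do so, record the trigger and the SpO2 at the first manoeuvre as well as the last means used.

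The cost is protocol wording and at most one or two form fields. Sample size and visits do not change. The timing rule belongs in the protocol because it governs what is done during the procedure; the event definition could be completed in the statistical analysis plan.
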